3.2 Known and Potential Risks and Benefits to Participants

3.2.1 Risks Associated with Rituximab

No dose-limiting adverse effects were observed in phase I-III trials that evaluated the safety and efficacy of rituximab in participants with lymphoma. The most commonly observed infusion-

related adverse effects were chills or rigors, fever, fatigue, headache, hypotension, nausea, leukopenia, angioedema, and pruritus. Fever, chills, headache, nausea, vomiting, rhinitis, and mild hypotension occurred primarily during rituximab infusions; these adverse events typically responded to interrupting and then resuming the infusion at a slower rate. Infusion reactions were seen in 1 (1%) patient with AAV who was treated with rituximab in the RAVE study (Stone et al., 2010). Details of the risks associated with rituximab treatment are described in rituximab prescribing information. Management of IRRs follows routine clinical protocols consistent with the prescribing information and the approved use of rituximab and obinutuzumab for other indications.

3.2.2 Risks Associated with Obinutuzumab

Risks associated with obinutuzumab treatment are described in the obinutuzumab Investigator's brochure Section 6.3. The most frequently observed adverse drug reactions in patients receiving obinutuzumab were infusion related reactions (IRRs) which occurred predominantly during infusion of the first 1000 mg. A decreased incidence of IRRs was observed after prevention of IRRs including adequate glucocorticoid, oral analgesic/anti-histamine, omission of antihypertensive medication was implemented. The incidence and severity of infusion-related symptoms decreased substantially after the first 1000 mg was infused, with most patients having no IRRs during subsequent administrations of obinutuzumab. Management of IRRs follows routine clinical protocols consistent with the prescribing information and the approved use of rituximab and obinutuzumab for other indications.

In the majority of patients, irrespective of indication, IRRs were mild to moderate and could be managed by the slowing or temporary halting of the first infusion, but severe and life-threatening IRRs requiring symptomatic treatment have also been reported. IRRs may be clinically indistinguishable from IgE-mediated allergic reactions (e.g., anaphylaxis). The rates of Grade 3-4 IRRs were similar before and after mitigation measures were implemented.

3.2.3 Data and Safety Monitoring Board (DSMB)

An independent DSMB will include 2 to 3 physicians who are rheumatologists or experts in a related field and a statistician. It is the DSMB's responsibility to weigh risks and benefits throughout the study's duration. Specifically, this role includes: monitoring evidence for treatment harm such as toxicity, adverse events, serious adverse events or deaths. The sponsor medical team will prepare the safety summary and participate in the safety review discussion.

The DSMB will convene for safety data review meetings after 10 patients have been treated and completed the 1-month visit (V4) and once every 6 months until the study completion. Records for adverse events, laboratory values, vital signs and disease status will be reviewed. The DSMB may recommend the study protocol be modified if major safety concerns occur.

3.3 Rationale for Study Design and Control Group

3.3.1 Rationale for the Study Design

Rituximab has been shown to be non-inferior to cyclophosphamide for patients with AAV in a randomized controlled trial Rituximab in ANCA-Associated Vasculitis (RAVE) trial (Stone et al., 2010). In the RAVE trial, 64% of the subjects in the rituximab group, compared to 53% in the cyclophosphamide group, achieving the primary outcome of complete remission at 24 weeks. In a subgroup analysis, rituximab treatment was superior to cyclophosphamide in PR3-ANCA positive patients, and this difference was statistically significant.

The subset of patients with PR3-AAV, which comprises approximately two thirds of patients evaluated in Western countries, represents the greatest unmet need in AAV. Results from the RAVE trial indicated that PR3-AAV patients had a higher rate of treatment failures and a higher percentage of severe relapses following successful remission induction, thus requiring frequent retreatment with glucocorticoids and other agents exposing patients to cumulative morbidity and organ damage from cumulative glucocorticoid exposure and disease activity. It is hypothesized that obinutuzumab may be superior to rituximab for the treatment of PR3-positive AAV patients based on the improved B-cell elimination potency and longer duration of B-cell depletion than that of rituximab.

This study is a randomized, double-blind, active-controlled trial to explore how obinutuzumab compares to rituximab for remission induction of PR3-AAV. The trial will also test the hypothesis that obinutuzumab treatment at baseline is associated with a longer time to relapse compared with rituximab treatment.

3.3.2 Rationale for the Dose Selection

In the RAVE protocol, rituximab therapy comprised 4 doses of rituximab 375 mg/m^2 per week in conjunction with glucocorticoids starting dose of 1 mg/kg/day and tapering to glucocorticoids free by month 5. This regimen has been modified to include two infusions of 1000 mg per dose 2 weeks apart on day 0 and day 14. The induction and follow up rituximab dose is planned as 1000 mg infusions. The rituximab regimen is selected based on the study by Jones et al. demonstrating that patients administered with 4 infusions of 375 mg/m^2 or 2 infusions of 1000 mg two weeks apart had comparable B cell depletion and similar rates of remission as a function of time in patients with refractory AAV (shown in Figure 2 below) (Jones et al., 2009). In addition, a recent study of comparison of two rituximab regimens for remission induction in ANCA-associated vasculitis showed a similar treatment effect whether rituximab was administered for 2 or 4 infusions. (Renard V. Abstract 2048 at American College of Rheumatology, November 2020).

Reducing the requirement for clinical visits without compromising the effectiveness of the treatment likely results in better treatment compliance.

3.3.3 Rationale for the 16-Week Glucocorticoid Tapering Schedule

A glucocorticoid tapering regimen that gradually reduces the prednisone dose from 60 mg per day on week 1 to 5 mg per day on week 13 to completely discontinues prednisone use by the end of week 16 is specified (section 5.6.2,). A multicenter survey of rituximab therapy for refractory of ANCA+ AAV patients demonstrated that the glucocorticoid taper of 4 months compared to the 5.5 months employed in the RAVE trial would not subject the patients to undue risk and will reduce the overall glucocorticoid use (Jones et al., 2009). The duration of the glucocorticoid taper will be extended to 16 weeks to maintain the goal of reducing the overall steroid use while

[figure not shown]

Figure 2 (Jones et al. *Arthritis & Rheumatism* Vol. 60, No. 7, July 2009, pp 2156–2168)

approximating the standard 4 to 6 months of glucocorticoids tapering schedule. The tapering schedule would be consistent with the 2009 European League Against Rheumatism (EULAR) recommendations for AAV to be between 7.5 mg and 10 mg of prednisolone after 3 months of treatment.

The investigator may increase the glucocorticoid dose if clinically indicated.

3.3.4 Selection of the Primary and the Key Secondary Endpoints

Patients diagnosed with PR3-AAV represent the greatest unmet need in AAV. The achievement of ANCA negativity following treatment is associated with long-term disease control, even though “cure” for PR3-AAV remains elusive. The achievement of sustained complete remission reduces patients’ risk from the combined threats of active AAV and complications of treatment, particularly glucocorticoids. (McClure et al., 2019; Specks et al., 2013; van Dam et al., 2020).

3.4 Study Duration and Dates

The remission induction period of the study includes up to 14 days of screening and 6 months of monitoring. The study maintenance period is 1 year after the 6-month induction period. The total duration of the study is approximately 18.5 months for each patient.

4 STUDY POPULATION SELECTION

4.1 Study Population

Thirty (30) patients with severe newly-diagnosed or recurring PR3-AAV are planned.

4.2 Inclusion Criteria

Each patient must meet the following criteria to be enrolled in this study.

1. Subjects aged 18 or greater.
2. Fulfillment of the definitions of the Second Chapel Hill Consensus Conference for ANCA-associated vasculitis (either granulomatosis with polyangiitis or microscopic polyangiitis).
3. Positivity for ANCA, directed against proteinase-3 (PR3).
4. Severe newly-diagnosed disease or severe relapsing disease. **Severe relapsing disease is defined as** at least one major BVAS/WG item or a score ≥ 3 and the investigator deems standard treatment for severe disease is necessary.
5. Minimum BVAS/WG of 3.
6. Relapsing patients must have B cells detectable in the peripheral blood.
7. Patients must have completed COVID-19 vaccination (per current recommended CDC guidelines) at least 4 weeks prior to enrollment. Patients who have recovered from COVID-19 prior to screening with a positive spike protein antibody test result but have not been vaccinated are also eligible.
8. Female subjects of childbearing potential who are not sterile must agree to use an acceptable method of contraception for 18 months after the last dose of infusion medication. Male subjects who are not sterile whose female partners are of childbearing potential must agree to use an acceptable method of contraception for 180 days after the last dose of infusion medication.
 - Females of childbearing potential include any female who has not undergone successful surgical sterilization (hysterectomy, bilateral tubal ligation, or bilateral oophorectomy) or is not postmenopausal (to be considered postmenopausal, the patient must have had amenorrhea for >12 consecutive months).
 - Acceptable methods of contraception include the use of at least two of the following: 1) intrauterine device; 2) hormonal contraceptives for at least 30 days prior to first dose infusion (oral, injectable, implant or ring); 3) barrier contraceptives (condom or diaphragm) with spermicide; or 4) abstinence.

4.3 Exclusion Criteria

Patients who present any of the following criteria will be excluded from the study.

1. Diagnosis with eosinophilic granulomatosis with polyangiitis (formerly Churg-Strauss syndrome) as defined by the Chapel Hill Consensus Conference.
2. Positive serum assays for ANCA directed against myeloperoxidase (MPO-ANCA)
3. Non-severe AAV, defined as disease that does not justify treatment with both B cell depletion and a four-month glucocorticoid taper.

4. Any of the co-morbidities:

- Allergies: a history of severe allergic reactions to human or chimeric monoclonal antibodies or murine protein.
- Infection (systemic): an active systemic infection at screening visit.
- Infection (deep space): have been diagnosed as having a deep-space infection, such as osteomyelitis, septic arthritis, or pneumonia complicated by empyema or lung abscesses, within 6 months prior to the screening visit.
- Infection (blood borne): active hepatitis B or active hepatitis C or a documented history of HIV, hepatitis B, or hepatitis C.
- Infection (history): History of recurrent significant infection or history of recurrent bacterial infections
- Liver disease: acute or chronic liver disease that is deemed sufficiently severe to impair their ability to participate in the trial.
- Renal disease: a history of documented anti-glomerular basement membrane disease (anti-GBM disease).
- Malignancy: Active or history of malignancy in the last 5 years. Individuals with squamous cell or basal cell skin carcinomas and individuals with cervical or ductal carcinoma in situ may be enrolled if they have received curative surgical treatment.
- Active COVID-19 infection.
- Uncontrolled disease: evidence of glucocorticoid dependent disease (such as asthma, COPD, psoriasis or IBD, etc.) requiring consistently greater than 10 mg of prednisone for disease control which might affect endpoint assessment or,
- Other uncontrolled diseases, including any uncontrolled psychiatric disorders, drug and alcohol abuse, that could interfere with participation in the trial according to the protocol.

5. Known diagnosis of human anti-chimeric antibodies (HACA) formation.

6. Subjects who are premenopausal and are:

- Pregnant on the basis of a serum pregnancy test,
- Breastfeeding, or
- Do not agree to use effective method(s) of contraception.

7. Use of prohibited medications: They have used any of the prohibited medication listed in Section 5.7.1.

8. Plasma exchange: They have been treated with plasma exchange within the 3 months preceding the screening visit.

9. History of intolerance to rituximab or other chimeric monoclonal antibodies (e.g., infliximab).

10. Recent vaccination: They have had a live vaccine fewer than 4 weeks (28 days) before or during randomization (vaccination with live vaccine through the end of study participation is contraindicated).

11. Daily use of non-steroidal anti-inflammatory drugs (NSAIDs)

12. Exclusion criteria related to laboratory parameters:

- a. Bone marrow suppression as evidenced by a total white count $< 4 \times 10^9 / \text{L}$, hemoglobin $< 7 \text{ gm/dL}$ or platelet count $< 100,000/\mu\text{L}$

- b. Aspartate aminotransferase or alanine aminotransferase or amylase > 2.5 times the upper limit of normal, unless attributed to vasculitis

5 STUDY TREATMENTS

5.1 Description of Treatments

5.1.1 Obinutuzumab

Obinutuzumab is a humanized and glycoengineered Type II anti-CD20 mAb of the IgG1 subclass. The molecular mass of the antibody is approximately 150 kDa. Obinutuzumab is provided as a single 1000 mg dose in a 50 mL glass vials containing 40 mL of 25 mg/mL liquid concentrate. In addition to the antibody, the liquid also contains histidine/histidine-HCl, trehalose, poloxamer 188 and water.

Obinutuzumab dosing solution will be prepared within 24 hours of scheduled dosing at 2°C to 8°C (36°F to 46°F) by diluting 40 mL (1000 mg) of obinutuzumab into a 250 mL 0.9% sodium chloride infusion bag.

5.1.2 Rituximab

Rituximab (RITUXAN) injection is a sterile, preservative-free, clear, colorless solution for intravenous infusion supplied as one 500 mg/50 mL (10 mg/mL) single-dose vial NDC 50242-053-06. Rituximab dosing solution will be prepared within 24 hours of scheduled dosing at 2°C to 8°C (36°F to 46°F) by diluting 1000 mg of rituximab into a 250 mL 0.9% sodium chloride infusion bag.

5.1.3 Infusion Solution

Obinutuzumab or rituximab does not contain antimicrobial preservatives. Therefore, care must be taken to ensure that the solution for infusion is not microbiologically compromised during preparation. If not used immediately, the prepared solution may be stored up to 24 hours at 2-8°C.

The infusion must be completed within 48 hours at room temperature ($\leq 30^{\circ}\text{C}/86^{\circ}\text{F}$) after the final dosing solution is prepared. No incompatibilities between obinutuzumab or rituximab and polyvinyl chloride or polyolefin infusion materials have been observed in concentration ranges from 0.4 mg/mL to 20.0 mg/mL after dilution.

5.2 Treatments Administered

5.2.1 Pre-Medication

Prior to start infusion, premedication with antihistamine (diphenhydramine 50mg) will be prescribed to reduce the potential infusion reactions. All patients will be prescribed with 650 mg to 1000 mg acetaminophen approximately 30 minutes before study drug infusion starts.

5.2.2 Obinutuzumab or Rituximab

Obinutuzumab or rituximab is administered via intravenous infusion at 1000 mg per dose. Patients will receive two doses of obinutuzumab or rituximab administered on day 0 and on day 14 (\pm 2 days).

First infusion: Administer at 50 mg/hr. The rate of the infusion can be escalated in 50 mg/hr increments every 30 minutes to a maximum of 400 mg/hr.

Subsequent infusions if no adverse events with first infusion: May start at 100 mg/hour and increase at 100 mg/hour every 30 minutes to maximum rate of 400 mg/hour if no adverse events occur.

5.2.3 Handling Potential Infusion Reactions

The handling of potential infusion reaction is outlined in the Investigator's Brochure and summarized below. If a patient experiences a reaction of any grade during infusion, adjust the infusion as the following:

- Grade 4 (life threatening): Stop infusion immediately and permanently discontinue dosing.
- Grade 3 (severe): Interrupt infusion and manage symptoms. Upon resolution of symptoms, consider restarting infusion at no more than half the previous rate (the rate being used at the time that the infusion reaction occurred) and, if patient does not experience any further infusion reaction symptoms, infusion rate escalation may resume at the increments and intervals as appropriate for the treatment cycle dose. Permanently discontinue treatment if patients experience a Grade 3 infusion related symptom at re-challenge.
- Grade 1-2 (mild to moderate): Reduce infusion rate or interrupt infusion and treat symptoms. Upon resolution of symptoms, continue or resume infusion and, if patient does not experience any further infusion reaction symptoms, infusion rate escalation may resume at the increments and intervals as appropriate for the treatment cycle dose.

The following medications may be used for infusion reactions as needed:

Drug	Dose	Indication
Acetaminophen 325 mg tablet	650 mg PO Q 4 hours prn	Infusion related reactions or temperature greater than 38 degree Celsius (100.4 F)
Diphenhydramine 25 mg/mL	25 mg IVPU Q 4 hours prn	Infusion related reactions; may repeat once if symptoms are not relieved within 15 minutes of initial dose.

Meperidine 25 mg/mL	25 mg IVPU Q 15 min, prn	Rigors, may repeat once (Max dose 50 mg)
Prochlorperazine 10 mg/mL	10 mg IVPU Q 6 hours, prn	Nausea and Vomiting

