6.3.9.10 Other Important Medical Events

HYPERSensitivity REACTIONS

Hypersensitivity reactions with immediate (e.g., anaphylaxis) and delayed onset (e.g., serum sickness), have been reported in patients treated with obinutuzumab. If a hypersensitivity reaction is suspected during or after an infusion (e.g., symptoms typically occurring after previous exposure and very rarely with the first infusion), the infusion should be stopped, and treatment permanently discontinued. Hypersensitivity may be clinically difficult to distinguish from infusion related reactions.

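### For a Grade 1-2 reaction with suspected hypersensitivity, 5.2.3 has the site continue or resume the infusion while 6.3.9.10 ends treatment for good, and no precedence is stated

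*Combined protocol and SAP*

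**What the plan says.** Section 5.2.3 sets its scope by severity and timing, not by cause: "If a patient experiences a reaction of any grade during infusion, adjust the infusion as the following". At Grade 1-2 the site slows or interrupts the infusion and treats symptoms. It then follows this step: "Upon resolution of symptoms, continue or resume infusion and, if patient does not experience any further infusion reaction symptoms", the rate may go up again on the usual schedule. At Grade 3 the site interrupts, manages symptoms, and may act on this: "Upon resolution of symptoms, consider restarting infusion at no more than half the previous rate". A second Grade 3 event at re-challenge ends treatment, as does any Grade 4 event. The section names one source: "The handling of potential infusion reaction is outlined in the Investigator's Brochure and summarized below". It does not mention hypersensitivity.

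Section 6.3.9.10, in the adverse event part of the protocol, starts from suspected cause: "If a hypersensitivity reaction is suspected during or after an infusion", then "the infusion should be stopped, and treatment permanently discontinued". It has no grade threshold. It gives a timing cue, "symptoms typically occurring after previous exposure and very rarely with the first infusion", and a caution, "Hypersensitivity may be clinically difficult to distinguish from infusion related reactions". It does not refer to 5.2.3.

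**The concern.** The two sections sort reactions on different axes, grade in one and suspected cause in the other, so the same event can be classified by both. When that happens at Grade 1-2 the instructions point in opposite directions.

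Staff handling a reaction would naturally turn to 5.2.3, because it is the dosing section and lists the rescue drugs. If symptoms settle on those drugs, 5.2.3 treats that as the signal to go on. A site following it to the letter would re-expose a patient whose treatment, under 6.3.9.10, should have ended. What is at stake is the safety of that patient, not the trial's inference.

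**Working it through.** No figure in the plan bears on this point, so there is nothing to recompute. The check is a comparison of texts.

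**Step 1. Can one event fall under both rules?** Section 6.3.9.9 defines an infusion related reaction as any adverse event during the infusion, or in the 24 hours after it, that the investigator attributes to study drug. A drug hypersensitivity reaction during the infusion meets that definition. Sections 3.2.2 and 6.3.9.10 both warn that the two kinds of reaction can be hard to tell apart at the bedside. So the overlap is real.

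**Step 2. What does each section require, grade by grade, when hypersensitivity is suspected during an infusion?**

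| Grade | 5.2.3 | 6.3.9.10 | Result |
|---|---|---|---|
| 1-2 | Slow or interrupt, treat, then continue or resume once symptoms resolve | Stop and discontinue for good | Direct conflict |
| 3, first event | Interrupt, then a restart may be considered at no more than half the rate | Stop and discontinue for good | 5.2.3 permits, but does not direct, what 6.3.9.10 rules out |
| 3, at re-challenge | Discontinue for good | Stop and discontinue for good | Agree |
| 4 | Stop and discontinue for good | Stop and discontinue for good | Agree |

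At Grade 1-2 the conflict can begin before symptoms resolve. 5.2.3 lets a slowed infusion keep running, whereas 6.3.9.10 says to stop it.

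**Step 3. Is precedence stated anywhere?** Neither section cites the other. Sections 3.2.1 and 3.2.2 refer the management of infusion reactions to routine clinical practice and the prescribing information, without a rule for suspected hypersensitivity. Section 6.3.9.9 gives the definition only. No precedence rule was found.

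**Step 4. Where could the case arise?** Section 6.3.9.10 associates hypersensitivity with earlier exposure. Every day-14 infusion is a re-exposure (5.2.2). Patients previously given an anti-CD20 agent may enter if B cells are detectable (5.7.1), so for some of them the first infusion may be one too. Treatment failures with detectable B cells are offered open-label obinutuzumab (3.1.2). Several provisions make the case rarer: the exclusions for severe antibody allergy and rituximab intolerance (4.3, 5.7.1), antihistamine and acetaminophen before infusion (5.2.1), and methylprednisolone (5.6.2). They remove known intolerance and dampen reactions, but do not say which instruction applies when one occurs.

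**Step 5. Which arm?** Section 6.3.9.10 describes reactions seen with obinutuzumab. The investigator is blinded (5.5), so in practice the stop rule has to be applied to either infusion.

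**The case against.** The best defence is that the sections have different triggers. 5.2.3 concerns infusion reactions. 6.3.9.10 applies only once the investigator suspects hypersensitivity, and the protocol lists hypersensitivity apart from infusion related reactions. A specific stop rule limiting a general management rule is an ordinary reading, and on that reading only a cross-reference is missing. The protocol also offers a way to separate the two: 3.2.2 places most infusion reactions in the first 1000 mg, while 6.3.9.10 places hypersensitivity mainly at later exposures. Delayed reactions fall outside 5.2.3 altogether. Finally, 5.2.3 is a summary of the Investigator's Brochure, and 3.2.1 and 3.2.2 point to the prescribing information. Any of these might settle the matter, and none is available here.

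Much of this stands. It narrows the problem to Grade 1-2 reactions, mostly at re-exposure, and it makes the override reading sensible. It does not remove the conflict. The protocol never states that reading, the scope of 5.2.3 is explicitly any grade, and the 6.3.9.9 definition puts a suspected drug hypersensitivity reaction inside the class that 5.2.3 manages. Even if the Brochure has a rule, the protocol's two sections should agree.

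A reader might infer more than the text supports in three ways:

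- **That the sections contradict each other at every grade.** The table shows they do not.
- **That the harm can be sized by the dose a patient misses when an infusion is stopped.** That dose is the result of obeying 6.3.9.10. The harm at issue is continued exposure, and the documents give nothing from which to quantify it.
- **That the primary comparison is at risk.** The modified intention-to-treat set (9.3.2) keeps anyone who received any study drug, so these patients are analyzed whichever instruction is followed.

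**Conclusion.** The concern holds for Grade 1-2 reactions during an infusion in which hypersensitivity is suspected. There 5.2.3, followed literally, gives the opposite instruction to 6.3.9.10, and the protocol does not say which prevails. At a first Grade 3 event there is tension but no contradiction, and at Grade 4 there is agreement.

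The number of patients affected cannot be estimated and may be zero. This is a minor patient-safety correction with no bearing on sample size, analysis sets or tests. The conclusion rests on the protocol text alone and assumes that sites have no overriding rule in the Investigator's Brochure, the prescribing information or local procedures.

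**What to change.** Add one sentence to 5.2.3, after checking it against the Investigator's Brochure:

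> *Exception: if a hypersensitivity reaction is suspected, at any grade, Section 6.3.9.10 governs. Stop the infusion and permanently discontinue study drug; do not resume under the Grade 1-3 steps. (Such reactions are expected mainly on re-exposure and seldom at a first infusion.)*

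The trigger should be suspicion alone. Requiring the site first to decide that the event is not an infusion related reaction would shut out the overlap case, since under 6.3.9.9 it is one. The timing cue is there to protect ordinary first-infusion reactions, which 3.2.2 describes as mostly mild to moderate and manageable by slowing or pausing.

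The sponsor should also state whether stopping blinded drug for this reason bars later open-label obinutuzumab. The answer is not obvious: the Introduction cites a report of three patients with this disease who tolerated obinutuzumab after anaphylaxis to rituximab.

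The cost is one sentence and a check of the Brochure. No visits, patients or CRF fields are added, because 5.8 already records why an infusion was discontinued. The downside is that an ordinary infusion reaction mistaken for hypersensitivity may occasionally end a patient's treatment for good. That risk already exists under 6.3.9.10, but the exception would make it more likely to be realized.
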